8.2 Study Assessments

8.2.1 Blood Tests and Urine Pregnancy Test

Blood will be taken via venipuncture at visit 1 and visit 2. At Visits 1 and 2, the levels of plasma lipids, insulin, beta-hydroxybutyrate, acetoacetate, and glucose will be measured. At Visit 1, U&Es and HbA1c will also be measured. These blood tests are purely for research purposes. No additional interventions should be needed due to the results and participants will adhere to their usual treatment plans (if applicable).

Participants will be administered a urine pregnancy test at their first study visit (if applicable).

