8.1 Study Visits

[figure not shown]
The assessments listed below will be carried out at each visit in the Advanced Imaging Centre at the Leeds General Infirmary. All participants, including the ones with T2D and heart failure, will continue taking their previously prescribed medications throughout the study.

Participants will be asked to attend 2 hospital visits. To minimise the inconvenience of hospital visits we will arrange transport. The first study visit will take up to 2.5 hours and the second visit will take up to 2.5 hours as well but 2 weeks later following adequate oral ketone loading. Participants will not need to fast for the visits.

[figure not shown]
Asymptomatic T2D patients with no history of heart disease, non- ischemic heart failure patients with LV ejection fraction <50% and healthy controls will undergo ³¹P-MRS and CMR scans over two visits (see study

Document: Research Protocol	
Short Title: KICK-Energy	Version 2.0
Chief Investigator: [name]	Date 09 Mar 2023
IRAS Project ID: 308642	Page 14 of 32

flowchart below).

Visit 1: All participants will undergo CMR and ³¹P-MRS studies at 3.0Tesla for evaluation of rest and dobutamine stress myocardial energetics, perfusion and function (see scan protocol below). In order to study the impact of ketosis on the myocardial energetic response to acute increases in cardiac workload, MR experiments will be conducted at rest and during haemodynamic stress (dobutamine stress). Blood samples will be obtained for measuring the levels of plasma beta-hydroxybutyrate, acetoacetate, and glucose.

Visit 2: ³¹P-MRS and CMR studies will be repeated after oral ketone supplementation to assess the impact of ketosis on myocardial energy metabolism, perfusion and function.

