The blood ketone level will be assessed and recorded on arrival. Ketosis will then be achieved via oral supplementation with ketone ester product Delta- G (BHB, TAS* Ltd), for 2 weeks three times daily between the 2 study visits. This product has been developed for commercial use by a University of Oxford spinoff company, TAS* Ltd and is available for use over the counter. The kinetics, safety and tolerability study of this product in healthy adults and in T2D patients suggested favourable results apart from mild gastrointestinal upset at higher doses^{37, 38}. While oral supplementation was not assessed in heart failure patients previously, another study assessed higher doses of ketone infusion in heart failure patients and demonstrated its safety³⁹.

Document: Research Protocol	
Short Title: KICK-Energy	Version 2.0
Chief Investigator: [name]	Date 09 Mar 2023
IRAS Project ID: 308642	Page 15 of 32

Baseline Assessments/Visit 1:

- Review of medical history and concomitant medications
- Review of history of diabetes and complications
- Review of inclusion/exclusion criteria
- Collection of demographic data (sex, ethnicity, age)
- Urine pregnancy test in women of childbearing potential
- Written informed consent
- Height, weight, waist, and hip circumferences
- 12-lead ECG
- Resting heart rate and blood pressure
- Venepuncture: 20mls of blood sample will be taken while inserting 2 venous lines (one
 line for dobutamine infusion and the other one for MRI contrast injection). This sample
 will be used for assessing blood ketone and glucose levels
- Multiparametric MRI
- Distribute 2 weeks supply of 25ml three times daily oral ketone ester product (Delta- G) supplementation
- Issue diaries and ketone finger prick test kits. The investigators will demonstrate how to
 perform the finger prick tests during this visit. In addition, the investigators will discuss
 how to keep the diary and answer any questions participants may have with regards to
 these tasks.

Study Visits:

Visit 2:

- 12-lead ECG
- Resting heart rate and blood pressure
- Venepuncture: 20mls and 2 venous lines (one line for dobutamine infusion and the other for MRI contrast injection).
- Small blood sample will be taken assess blood ketone and glucose levels
- Multiparametric MRI
- Collect and review diaries

End of the study.

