8.4 Discontinuation/Withdrawal of Participants

Each participant has the right to withdraw from the trial at any time. In addition, the Investigator may discontinue a participant from the trial at any time if the Investigator considers it necessary for any reason including:

- Pregnancy
- Ineligibility (either arising during the trial or retrospectively having been overlooked at screening)
- Significant protocol deviation
- An adverse event to gadolinium contrast or dobutamine injection during the baseline visit
- Withdrawal of Consent

Document: Research Protocol	
Short Title: KICK-Energy	Version 2.0
Chief Investigator: [name]	Date 09 Mar 2023
IRAS Project ID: 308642	Page 19 of 32

Where patients wish to withdraw from the study, clarification of the extent of withdrawal will be sought and documented in the CRF. Patients who withdraw from the study will be replaced.

If the participant is withdrawn due to an adverse event, the Investigator will arrange for follow-up visits or telephone calls until the adverse event has resolved or stabilised.

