8.5 Definition of End of Study

The end of trial is the date of the last visit of the last participant.

9 Safety Reporting

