9.6 Procedures for Recording Adverse Events

The patient information sheets will include all possible adverse events relevant to MR scans and ketone supplementation. Potential risks are outlined in section 8.2.4.

All AEs occurring during the study that are observed by the Investigator or reported by the participant, will be recorded on the CRF, whether or not attributed to study investigations.

The following information will be recorded: description, date of onset and end date, severity, assessment of relatedness to trial medication, other suspect drug or device and action taken. Follow-up information should be provided as necessary.

The severity of events will be assessed on the following scale: 1 = mild, 2 = moderate, 3 = severe.

AEs considered related to the study assessments as judged by a medically qualified investigator or the Sponsor will be followed either until resolution or the event is considered stable.

It will be left to the Investigator's clinical judgment to decide whether or not an AE is of sufficient severity to require the participant's removal from the study. A participant may also voluntarily withdraw from the study due to what he or she perceives as an intolerable AE. If either of these occurs, the participant must undergo an end of trial assessment and be given appropriate care under medical supervision until symptoms cease, or the condition becomes stable.

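### Visit 2 repeats the dobutamine and contrast exposures without a scheduled pregnancy test or eligibility review, and the protocol does not say when adverse-event collection ends after that visit

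*Protocol*

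**What the plan says.** **Checks before exposure.** Section 8.2.1 fixes the timing of the test: "Participants will be administered a urine pregnancy test at their first study visit (if applicable"). The Visit 1 list in section 8.1 has the matching entry, "Urine pregnancy test in women of childbearing potential", together with reviews of the inclusion and exclusion criteria and of concomitant medication. The Visit 2 list has an ECG, heart rate and blood pressure, venepuncture, blood sampling, the MRI and the entry "Collect and review diaries". It contains none of the three checks and no adverse-event enquiry.

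**Exposure at Visit 2.** Section 8.1 says the "MRS and CMR studies will be repeated after oral ketone supplementation to assess the impact of ketosis", and the Visit 2 list requires "Venepuncture: 20mls and 2 venous lines (one line for dobutamine infusion and the other for MRI contrast injection"). Section 8.2.2 describes a single scan protocol. Dobutamine is infused for spectroscopy and cine imaging and again for stress perfusion, and contrast is injected once for stress and once for rest perfusion.

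**Eligibility.** Sections 7.1, 7.2 and 7.3 each exclude women who are pregnant, lactating or planning a pregnancy while the study runs. Section 8.4 lists pregnancy, and ineligibility that arises after entry, among the reasons for discontinuation.

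**Adverse-event period.** Section 9.6 records "All AEs occurring during the study that are observed by the Investigator or reported by the participant". Section 6 makes Visit 2 the final hospital visit, within 2 weeks of the first, but allows up to 4 weeks in the study. The Visit 2 list in section 8.1 closes by declaring the study over. Section 8.5 adds: "The end of trial is the date of the last visit of the last participant".

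**The concern.** The protocol treats pregnancy as a status that can change after entry, since it is both an exclusion and a reason to stop. Yet it schedules a check before only one of two equivalent exposure sessions. A woman who conceived between the visits, or too recently before Visit 1 to test positive, could receive a second set of infusions and contrast injections without any planned step that would show it. The general eligibility review has the same gap.

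The second issue is the capture of safety data. A reaction that starts after Visit 1 can be reported when the participant returns. A reaction that starts after the participant leaves Visit 2 has no planned point of capture, and the text does not settle whether it would still count as occurring in the study. Sections 4.1, 8.1 and 8.2.4 all state that the oral product had not been assessed in heart failure patients before, so complete capture matters more here than in a study of a familiar exposure.

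**Working it through.** The protocol gives no figure on this point, so there is none to reproduce. The check is a comparison of the two visits followed by a count.

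**1. The two visits side by side (sections 8.1, 8.2.1, 8.2.2)**

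| Item | Visit 1 | Visit 2 |
|---|---|---|
| Dobutamine infusions | 2 | 2 |
| Gadolinium boluses | 2 | 2 |
| Urine pregnancy test, where applicable | listed | not listed |
| Eligibility review | listed | not listed |
| Concomitant medication review | listed | not listed |
| Adverse-event enquiry | not listed | not listed |
| Later scheduled contact | Visit 2 | none |

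**2. Total exposures.** Inputs are 30 + 30 + 30 = 90 participants (section 6) and 2 infusions + 2 boluses = 4 exposures per visit (section 8.2.2).

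- Each visit, full attendance: 90 × 4 = 360.
- Both visits: 720, so Visit 2 carries 360/720 = 50%.
- If 25 per group reach Visit 2 (the group size in the section 10 power calculation, applied here by assumption to all three groups): 75 × 4 = 300, and 300/(360 + 300) = 45%.

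**3. Exposures affected by the missing pregnancy test.** The test applies only to women of childbearing potential. The protocol does not give their share p, so p is an assumption. With full attendance, the affected share of all exposures is p × 360/720 = p/2.

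| Assumed p | Women | Visit 2 exposures | Share of 720 |
|---|---|---|---|
| 10% | 9 | 36 | 5% |
| 30% | 27 | 108 | 15% |
| 50% | 45 | 180 | 25% |

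With 75 at Visit 2 and the same p, the factor is 300/660 in place of 1/2. The shares become about 4.5%, 13.6% and 22.7%.

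**4. The adverse-event window.**

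- Section 8.1 reads as though a participant's study closes at Visit 2.
- Section 6 puts Visit 2 within 2 weeks but allows 4 weeks in all, which leaves at least 4 − 2 = 2 weeks unaccounted for.
- Section 8.5 defines the end for the trial as a whole, not for each participant.
- Section 9.6 ties recording to the study period without saying which of these applies.

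The closing date is therefore undefined for each participant. No contact is scheduled after Visit 2 on any of the readings.

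**The case against.** The protocol is not empty on safety. Section 9.6 already requires every adverse event observed or reported to be recorded, so a separate enquiry line at Visit 2 is partly a matter of drafting. Medically qualified staff attend the visits, participants hold the investigators' contact details, women planning pregnancy are excluded, and the investigator may discontinue anyone at any time. Safety is not a listed endpoint, so no primary or secondary result changes. All of this stands, and it limits the point. It does not supply a scheduled check before the second exposure or a defined end to collection. The 24-hour access in section 8.2.4 is tied to nausea during the ketone course. Section 11.1 says data are spread over all visits, but that general sentence also covers demographics and does not amend the specific Visit 2 list.

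A reader might infer more than the documents support:

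- **Half of all exposures go unchecked for pregnancy.** Visit 2 carries half the exposures, but the test never applied to most groups of participants in full. It concerns women of childbearing potential only.
- **Collection lasts 14 days after Visit 1 and 0 days after Visit 2.** Nothing says the diary collects adverse events. Section 8.1 mentions it alongside the finger-prick kits. The 4-week maximum also means the window after Visit 2 is undefined, not shown to be zero.
- **Sections 9.5 and 9.7 are contradicted.** They govern follow-up of events already identified, including those seen at Visit 2. They do not address how new events are found.
- **Section 8.4 limits discontinuation for reactions to the first session**, because it lists "An adverse event to gadolinium contrast or dobutamine injection during the baseline visit". The list is introduced as non-exhaustive, and little remains to discontinue at the final visit.
- **Later events are bound to be missed.** Spontaneous reports remain possible. What is lacking is a scheduled means of capture.

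**Conclusion.** The concern holds in two limited parts. First, the pregnancy test and the eligibility review are scheduled only before the Visit 1 exposures, while Visit 2 repeats both infusions and both boluses. This sits badly with the protocol's own exclusion and discontinuation criteria. The pregnancy-test part touches roughly 5% to 25% of all exposures, on the assumption that women of childbearing potential are 10% to 50% of participants and that all attend. The number could be smaller, and the count measures exposures without a check, not harm. Second, the protocol neither states when a participant's adverse-event collection ends nor schedules a contact that would capture events beginning after Visit 2.

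Neither part affects the efficacy analysis. Visit schedules and the adverse-event period belong in a protocol and would not normally be left to a statistical analysis plan. This is an inexpensive improvement to safety oversight and safety data, not a flaw in the study's main comparison.

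**What to change.** 1. Reconcile the Visit 2 list in section 8.1 and the test timing in section 8.2.1 with the exclusions in sections 7.1 to 7.3 and with section 8.4. The checks the protocol makes before the Visit 1 exposures (pregnancy test where applicable, eligibility review, concomitant medication review) would then also be scheduled at Visit 2, with an adverse-event enquiry added. What follows from a result is for the investigators and sponsor to settle when they reconcile these sections.
2. Reconcile sections 6, 8.1, 8.5 and 9.6 by stating when each participant's adverse-event collection ends. One short telephone contact after Visit 2 fits inside the 4-week maximum already in section 6. Section 8.5 should agree with the date chosen.

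The cost is a urine test for the women concerned (9 to 45 tests on the assumed shares), a few minutes at Visit 2, and one call per participant, or 90 calls if all attend. No extra hospital visit is needed.

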8.2.2 Multiparametic MRI

³¹P-MRS (3-Tesla): ³¹P-MRS will be performed to obtain the rest and dobutamine stress PCr/ATP from a voxel placed in the mid-ventricular septum, with the subjects lying supine with the ³¹P coil placed over their heart, in the iso-centre of the magnet⁴⁶⁻⁴⁸.

After the resting 3-dimensional chemical shift imaging ^{31}P -MRS and resting short-axis stack are acquired, dobutamine will be infused intravenously at incremental rates from 5 to a maximum of 40 μ g/kg with a target of 65% of age maximal heart rate. During this time, blood pressure will be measured every minute. Heart rate, blood pressure, pulse oximetry will be monitored continuously during both dobutamine infusion studies. Heart rate will then be maintained at target for the duration of the scans (8 minutes 29 seconds for ^{31}P -MRS, 5 minutes for short-axis cine imaging).

CMR (3-Tesla): CMR will include pilot and cine imaging to assess LV volumes, mass and ejection fraction, myocardial strain parameters. Dobutamine (5 to 40 µg/kg/min rate increased in a staged incremental fashion) will then be infused again for at least 3 minutes. Subsequently, gadolinium-based contrast (Gadovist®, Bayer Pharma, Berlin, Germany) will be injected for first-pass perfusion imaging (39). Dobutamine will then be discontinued and, after at least 20 minutes to allow washout, another bolus of gadolinium (0.075 mmol/kg) will be given for rest perfusion imaging. Data acquisition will use a multi-slice, free-breathing, saturation recovery pulse sequence with fast low angle shot (FLASH) readout, acquired over 60 heartbeats. In the first three beats proton density weighted images (without saturation preparation) will be acquired. Arterial input function (AIF) data will be obtained from interleaved low-resolution images (dual-sequence method) in a single slice with dual-echo acquisition to allow correction of T2* related signal loss. Late gadolinium enhancement (LGE) in matching LV short- and long-axis planes will be carried out more than 8 minutes after rest perfusion imaging. Total scan time for the CMR is c. 1 hour.

With participant's permission, CMR results will be shared with the participant's GP for the T2D and heart failure patients and the healthy volunteers. If the CMR detects any unexpected abnormalities (such as

Document: Research Protocol	
Short Title: KICK-Energy	Version 2.0
Chief Investigator: [name]	Date 09 Mar 2023
IRAS Project ID: 308642	Page 17 of 32

previous myocardial infarction, features of cardiomyopathy etc.), urgent cardiology review will be organised as an outpatient.

Any other incidental findings picked up on the scans not concerning the heart will be reported to the GP for further investigation if required.

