2 SYNOPSIS

Study Title	Ketone supplementation to Improve Cardiac Energetics and Function	
Study Design	Single centre, prospective case control study.	
Study Participants Adult T2D patients, adult heart failure patients and healthy adults.		
Planned Sample Size	30 T2D patients 30 healthy individuals with no diabetes 30 adults with non-ischemic heart failure with systolic heart failure (ejection fraction <50%)	
Planned Study Period	07/08/2022 to 01/08/2025 for 36 months	
Primary Aim To advance our understanding of the physiological effects of myocardial energetic impairment, perfusion and cardiac contractile T2D and heart failure patients.		

Document: Research Protocol	
Short Title: KICK-Energy	Version 2.0
Chief Investigator: [name]	Date 09 Mar 2023
IRAS Project ID: 308642	Page 4 of 32

Objectives	Primary objective: Change in myocardial rest and dobutamine stress PCr/ATF	
	following 2 weeks of oral ketone ester supplementation (delta G three times daily).	
	Secondary objectives: Following oral ketone ester supplementation, changes in:	
	1) myocardial perfusion,	
	2) LVEF at rest; and during dobutamine stress;	
	3) Myocardial strain (systolic strain and diastolic strain rate).	
Primary Endpoint	Change in myocardial energetics during rest and dobutamine stress before and after oral ketone ester supplementation.	
Secondary Endpoints	Following oral ketone ester supplementation, changes in:	
	i) myocardial rest PCr/ATP,	
	ii) myocardial perfusion,	
	iii) left ventricular ejection fraction (LVEF) at rest;	
	iv) LVEF during dobutamine stress.	

Document: Research Protocol	
Short Title: KICK-Energy	Version 2.0
Chief Investigator: [name]	Date 09 Mar 2023
IRAS Project ID: 308642	Page 5 of 32

3 Abbreviations

AE Adverse event
AR Adverse reaction

ATP Adenosine triphosphate

CF Consent form
CI Chief Investigator
CRF Case Report Form

CMR Cardiac Magnetic Resonance scan (MRI scan of the heart)

CT Computed Tomography

DM Diabetes Mellitus

ECG Electrocardiogram

GCP Good Clinical Practice

GP General Practitioner

HbA1c Glycated hemoglobin

FA Fatty Acid

ICF Informed Consent Form

LV Left ventricle

MRS Magnetic resonance spectroscopy

MS Mass Spectroscopy

NHS National Health Service

PCr Phosphocreatine ³¹P-MR Phosphorus MR

PI Principal Investigator

PIL/S Participant/ Patient Information Leaflet/Sheet

R&I NHS Trust R&I Department
REC Research Ethics Committee
SAE Serious Adverse Event

SAE Serious Adverse Event
SAR Serious Adverse Reaction

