8.2.4 Potential risks and hazards

MR is safe, with no known risks. The contrast medication is safe, but rarely reactions may occur. The department is equipped to cope with allergic reactions if they happen. Dobutamine can cause breathlessness and chest discomfort, subsiding within minutes of the medication being stopped. Oral Ketone supplements are safe and should not cause any significant side effects at the recommended doses. Mild nausea might be experienced by the participants, they will therefore be fully informed of this potential side effect. Participants will be provided 24hour access to investigators and will be asked to contact the study team directly should they experience this side effect. The investigators, who are medically qualified NHS doctors, will organise an urgent review (within 24 hours) and assess the participants with physical examination. Participants will be asked to hold the next dose of ketone ester until they have been reviewed. Patients will be monitored and cardiology team will be present during the CMR studies. The oral ketones have been safely administered to patients with diabetes. While oral supplementation was not assessed in heart failure patients previously, another study assessed higher doses of ketone infusion in heart failure patients and demonstrated its safety³⁹.

Ketones are naturally produced energy fuels by the liver. Ketones have been safely delivered per orally with no complications in healthy volunteers and intravenously even in patients with severe heart failure^{39,}
⁴⁹. Ketone will be delivered via per oral administration for a course of 2 weeks in the form of a ketone ester drink three times daily. No side effects are expected at this dose and duration in the patients or controls.

During the scan acquisitions, participants will also hold a buzzer in their dominant hand and will be able to use the buzzer to attract attention immediately for any reason while in the scanner. The study investigators are all medically qualified stuff (consultant cardiologists or cardiology trainees and nurses) who will be present at all times during the research visits, which will be conducted in an hospital environment.

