10.1 The Level of Statistical Significance

Statistical significance will be considered at P value of 5% significance and a power of 90%.

10.2 Procedure for Accounting for Missing, Unused, and Spurious Data.

Spurious and missing data will lead to data from that participant being excluded from the study.

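### Under section 10.2 a failed dobutamine stress scan also removes the participant's valid rest PCr/ATP, and the protocol does not say how a below-target stress scan is treated

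*Protocol*

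**What the plan says.** The primary endpoint in the synopsis (section 2) covers both states: "Change in myocardial energetics during rest and dobutamine stress before and after oral ketone ester supplementation". Section 5.1 likewise names rest and dobutamine-stress PCr/ATP together.

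Section 8.2.2 acquires the resting spectrum and the resting short-axis stack first. Then "dobutamine will be infused intravenously at incremental rates from 5 to a maximum of 40" µg/kg, "with a target of 65% of age maximal heart rate". It continues: "Heart rate will then be maintained at target for the duration of the scans", which is 8 min 29 s for the spectrum and 5 min for the cines. It has no branch for a target that is not reached or not held.

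Under section 8.1 all participants, including those with T2D and heart failure, "will continue taking their previously prescribed medications throughout the study".

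Section 8.2.4 notes: "Dobutamine can cause breathlessness and chest discomfort, subsiding within minutes of the medication being stopped".

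Section 8.4 lets the investigator discontinue a participant at any time for any reason. Its examples include a significant protocol deviation and "An adverse event to gadolinium contrast or dobutamine injection during the baseline visit". Patients who withdraw are replaced.

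Section 10.2 contains the only data-handling rule: "Spurious and missing data will lead to data from that participant being excluded from the study".

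**The concern.** The stress scan is the more fragile half of the primary measurement. It needs a target heart rate, held for over eight minutes, at two visits. The rest scan needs no dobutamine at all. Section 10.2 nevertheless ties them together: one unusable stress acquisition at either visit takes the whole participant out, rest pair included.

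Two things are at stake. The first is precision, because valid primary-objective data are thrown away. The second is selection. Those who remain are the participants who tolerated and responded to dobutamine at both visits, and the second of those visits comes after supplementation. Replacing excluded participants would restore the number but not remove the selection.

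The silence on below-target scans adds to this. Section 10.2 turns on whether a scan counts as spurious, and nothing says whether missing the heart-rate target makes it so. Two readers could therefore build different primary datasets from the same scans.

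**Working it through.** **Inputs from the protocol.** Section 10 gives an effect of 0.18 on stress PCr/ATP, SD 0.26, 5% significance, 90% power, 25 per group needed and 30 recruited, with two-tailed paired t-tests. The share of participants who miss the target is not given, so a range is used.

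**The plan's own figure.** Take 0.26 as the SD of the within-person change. The paired t-test then has noncentrality (0.18/0.26) × √n. Two-sided 5% power from the noncentral t is 90.1% at n = 24 and 91.3% at n = 25, so 25 reproduces on this reading. (It does not reproduce on the one-way ANOVA that the text names: two independent groups of 25 give 67%. That is a separate point.)

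**When the reserve is used up.** Let q be the chance that a stress scan fails at a given visit, with no other loss and no replacement.

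- Failures independent between visits: 30 × (1 − q)² = 25, so q = 1 − √(25/30) = 8.7%.
- Failures fully shared (the same people fail at both visits): 30 × (1 − q) = 25, so q = 5/30 = 16.7%.

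**Complete pairs under whole-participant exclusion.** P(≥25) is the binomial probability that at least 25 of 30 remain, with retention (1 − q)² or (1 − q).

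| q per visit | Expected pairs, independent | P(≥25) | Expected pairs, shared | P(≥25) |
|---|---|---|---|---|
| 10% | 24.3 | 48% | 27.0 | 93% |
| 15% | 21.7 | 12% | 25.5 | 71% |
| 20% | 19.2 | 2% | 24.0 | 43% |

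**Power for 0.18 on stress PCr/ATP** (SD of change 0.26): n = 27, 93%; n = 25, 91%; n = 24, 90%; n = 20, 84%; n = 19, 81%. At q = 20% power is therefore about 90% if failures are shared and about 81% if they are independent.

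**The rest comparison.** Under 10.2 it falls to the same n, although all 30 rest pairs could be valid. If exclusion were by endpoint, rest would keep up to 30 pairs at every q in the table. The protocol gives no effect size or SD of change for rest PCr/ATP, so no rest power is computed.

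**The case against.** **A scoring rule for off-target scans is commonly left to the SAP, which is not shown.** This stands in large part, and the absence of a detailed rule or of sensitivity sets is not the main point here. But the exclusion rule is already fixed in 10.2 of the protocol. An SAP that kept the rest pair would contradict it.

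**A reader might infer that some participants cannot reach the target.** The documents do not support this. They give no attainment rate and name no rate-limiting drug, 65% is a submaximal target, and the infusion is titrated upwards towards it. Section 8.2.4 says that symptoms subside after dobutamine is stopped; it does not say that symptoms lead to stopping. Only a possible shortfall can be claimed.

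**A reader might infer that a dobutamine event at Visit 2 has no provision.** That goes too far. The baseline-visit event in 8.4 is one example under a general power to discontinue at any time, and a significant protocol deviation is another. Section 9.6 also covers removal for an adverse event. These routes are discretionary and do not name a missed target, but they mean that pooling and exclusion are not the only possible outcomes.

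**A reader might infer that below-target scans at Visit 2 would imitate a ketone benefit.** Section 4.1 says that PCr falls when ATP demand exceeds synthesis, which gives a direction but no graded response. Any size would need a rest-to-stress fall, a workload relation and a rate of Visit-2-only failure, none of which is in the protocol. With the same person, the same cap and continued medication, similar shortfalls at both visits are at least as plausible, and these would largely cancel in a within-person change.

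**The loss may be small.** This stands at low failure rates or where failures are shared. The independent column above is the pessimistic end.

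**Conclusion.** The point holds in limited form. Section 10.2 would discard a valid rest PCr/ATP pair because of a stress acquisition that is absent, incomplete or judged spurious, and the protocol leaves open whether a below-target spectrum counts as spurious.

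The size is conditional. The reserve is used up somewhere between 8.7% and 16.7% failure per visit. At 20% failure per visit, power for the stress effect is between about 81% and 90%. These figures assume no replacement and no other loss. They also take 0.26 as the SD of change, which corresponds to a between-visit correlation of 0.5 if 0.26 is the SD at each visit. The failure rate itself is unknown, so no claim is made that power will fall below plan.

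The case for the change does not rest on that rate: excluding by endpoint keeps valid primary-objective data at any rate and costs almost nothing.

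**What to change.** 1. In 10.2, state that missing or spurious data remove only the affected endpoint. Rest PCr/ATP and every other valid pair stay in the analysis.
2. In 8.2.2 and 10, state that technically valid stress spectra at both visits are analysed whether or not the heart-rate target was reached. Record achieved heart rate and blood pressure at both visits, and report the number below target or stopped early by group and visit.
3. Add a sensitivity analysis limited to pairs at target at both visits. It should not be primary, since it selects on a response measured after supplementation.
4. Treat any adjustment for achieved rate-pressure product as exploratory only. It too is measured after supplementation, and the hypothesis is that ketones improve contractile function, so adjustment could remove part of the effect.

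The cost is a few sentences. Heart rate and blood pressure are already monitored during the infusion. Rest and stress results will rest on different numbers of participants, which must be reported, and keeping below-target scans brings some variation in workload into the stress comparison. Item 1 does not recover a stress pair that was never acquired. No dose, heart-rate target or stopping rule changes.
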